5.6 Management of Participants Who Become Pregnant

Pregnant women and women who plan to become pregnant during the first 24 weeks after study vaccine administration are excluded from enrollment. If a participant becomes pregnant during

the course of the study, they will continue to be followed for the remainder of the study period per protocol SOE; however, for all subsequent study visits, blood draws will be limited to safety tests only (samples for research immunology will not be drawn). Full blood draws can resume post-pregnancy or post-abortion only if deemed safe for the participant, per the clinical judgment of the PI in consultation with the IND Medical Officer. The PI or designated AI will be responsible for reporting any pregnancy. New pregnancies will be reviewed weekly in aggregate with other safety data and forwarded as necessary to IRBs and study sponsors.

If a participant becomes pregnant within 24 weeks after the study vaccination, every effort will be made to remain in contact with the pregnant participant to record the outcome of pregnancy for the study database. Pregnancy outcomes will be recorded via a standardized pregnancy CRF. Information documented on this form will include date of last menstrual period, date pregnancy confirmed, history of complications during prior pregnancies (such as congenital abnormalities or spontaneous abortions). A separate pregnancy outcome CRF will be completed for the outcome of the pregnancy including date of termination or delivery, any complications of pregnancy, the gender, weight, presence of any congenital abnormalities, APGAR score, other complications of delivery and the status of the child.

Reporting outcomes of pregnancies that begin later than 24 weeks is not required by the IND Sponsor, nor is there an IND Sponsor requirement for annual evaluation requirement for children born to vaccine recipients. However, all children conceived within 24 weeks post-vaccination and born to vaccine recipients will be annually evaluated for a minimum of 2 years to meet requirements set by regulatory authorities in Uganda. After termination of the study, the site will be solely responsible for maintaining and reporting applicable data obtained in this long-term follow-up.

5.7 Management of Participants Who Become Incarcerated

Participation of prisoners is not planned and any participant will be suspended from study visits while incarcerated, except visits or telephone contact for the purpose of ensuring participant safety. The IRB will be notified of the period of incarceration and safety assessments to be conducted. Data and samples that were collected before the period of incarceration may still be stored and used for analyses. After release from incarceration, the participant may either return to participation in study visits according to the SOE or study participation may be terminated at the discretion of the PI.

Participants who have returned to the clinic after a period of incarceration of more than 12 months will review pertinent sections of the consent form with a study staff. A note to the effect that the review was done will be written in the progress notes in the participant's binder.

5.8 Management and Counseling of Participants with Positive HIV or Syphilis Test

Participants found to be infected with HIV or syphilis at screening will be counseled appropriately by a study physician/nurse and referred to a local healthcare facility for care or treatment.

6.0 PHARMACY AND VACCINE ADMINISTRATION PROCEDURES

Study treatment is defined as VRC-EBOADC086-00-VP (cAd3-EBO S). Refer to the Investigator's Brochure for further information about the study agent.

6.1 Regimens

Forty healthy adult volunteers in the Kampala area, ages 18-50 years, will be enrolled into one of two groups of 20 participants each as shown in Table 1. Participants in Group 1 will receive a single injection IM of cAd3-EBO S at 1×10^{10} PU and participants in Group 2 will receive a single injection of cAd3-EBO S at 1×10^{11} PU.

6.2 Study Product Formulation, Preparation, and Storage

6.2.1 Formulation

The drug substance was manufactured by Advent S.r.l. (Pomezia, Italy, a subsidiary of Okarios, Inc.) and the vaccine, VRC-EBOADC086-00-VP (cAd3-EBO S) and diluent were manufactured at the VRC Pilot Plant (VPP) operated by the Vaccine Clinical Materials Program (VCMP), Leidos Biomedical Research Inc., Frederick, MD (formerly SAIC-Frederick, MD), according to cGMP regulations. The drug product is a sterile, aqueous, buffered solution composed of cAd3-EBO S drug substance filled into single dose vials at 1×10^{11} PU/mL. Vials are aseptically filled under cGMP to a nominal fill volume of $1.2 \text{ mL} \pm 0.1 \text{ mL}$ to allow withdrawal of 1.0 mL for IM administration. Vials are intended for single use only and thus do not contain a preservative. Additional details on VRC-EBOADC086-00-VP (cAd3-EBO S) composition and manufacturing can be found in the Investigator Brochure.

The diluent, VRC-DILADC065-00-VP, was manufactured at the VPP. It is comprised of the formulation buffer and will be used to dilute the cAd3-EBO S vaccine to prepare the 1×10^{10} PU/mL dosage to be administered in this study. The formulation buffer is pH 7.4 and consists of 10 mM Tris, 10 mM Histidine, 5% Sucrose (w/v), 75 mM Sodium Chloride, 1 mM Magnesium Chloride, 0.02% Polysorbate 80 (PS-80) (w/v), 0.1 mM EDTA, and 0.5% (v/v) Ethanol. The diluent is supplied in glass vials at a nominal fill volume of $1.2 \text{ mL} \pm 0.1 \text{ mL}$ to allow withdrawal of 1.0 mL. Vaccine dose levels are achieved by administering the appropriate volume directly from the vial or dilution to the appropriate dosage. Additional diluent VRC-DILADC065-00-VP composition and manufacturing information can be found in the Investigator Brochure.

6.2.2 Study Product Labels

The labels for VRC-EBOADC086-00-VP (cAd3-EBO S) and VRC-DILADC065-00-VP, diluent, will have specific product information (e.g., part number, lot number, fill volume, storage temperature) included on the product vial labels. The vaccine label will contain an Investigational Use Statement ("Caution: Limited by Federal Law to Investigational Use"), and manufacturer information.

6.2.3 Study Product Storage

VRC-EBOADC086-00-VP (cAd3-EBO S) will be stored at $\leq -60^{\circ}\text{C}$, and VRC-DILADC065-00-VP (diluent) will be stored at -45°C to -10°C , each in a qualified, continuously monitored, temperature-controlled freezer.

If deviations in storage temperature occur from the normal allowance for the pharmacy freezer, the site pharmacist must report the storage temperature excursion promptly to the PI and the IND sponsor. The excursion must be evaluated and investigated and action must be taken to restore and maintain the desired temperature limits. Following the outcome of the investigation, the IND sponsor will notify the pharmacist if continued clinical use of the product is acceptable.

6.2.4 Preparation of Study Product for Injection

To prepare the vaccine for injection, the vial containing cAd3-EBO S and/or diluent will be thawed at ambient temperature ($15\text{-}25^{\circ}\text{C}$).

Preparation will be done in a clean preparation biosafety hood with limited access. Only the required vials will be present in the preparation unit during dilution, and medication labels should be strictly segregated to avoid mix-ups. All injections will be administered IM into the deltoid muscle by needle and syringe and must be administered within 4 hours after removing the vaccine vial from the freezer.

Product dilutions will be prepared in a Class II biosafety cabinet.

Preparation of VRC-EBOADC086-00-VP (cAd3-EBO S) at 1×10^{10} PU Dose

Preparation of the 1×10^{10} PU dosage of cAd3-EBO S requires one serial dilution. Remove one vial of cAd3-EBO S vaccine and two vials of diluent from the freezer and allow them to equilibrate to room temperature. Using sterile syringes, draw up 1.0 mL of diluent from one diluent vial and 0.35 mL from the other diluent vial and inject these volumes into a sterile vial. Then, using a sterile syringe draw up 0.15 mL of the 1×10^{11} PU/mL vaccine and inject this into the vial with the diluent to achieve a total volume of 1.5 mL. Vortex the vial at half speed for 3-5 seconds. This vial now contains 1.5×10^{10} PU cAd3-EBO S in 1.5 mL and has a concentration of 1×10^{10} PU/mL. One 1 mL injection of this preparation will be administered for each dose. Discard remnant vaccine in vial in a biohazard container for incineration.

Preparation of VRC-EBOADC086-00-VP (cAd3-EBO S) at 1×10^{11} PU Dose

No dilution is needed for preparation of the 1×10^{11} PU dosage of cAd3-EBO S vaccine. Remove one vial of vaccine from the freezer and allow it to equilibrate to room temperature in a biosafety hood. Using a sterile syringe, withdraw 1.0 mL from the vial. One 1 mL injection of the preparation will be administered. Discard remnant vaccine in a vial in a biohazard container for incineration.

6.3 Pharmacy: Product Supply, Distribution, and Accountability

6.3.1 Study Product Acquisition/Distribution

The study product(s) for this protocol are supplied by the Vaccine Research Center, NIH and should be obtained by following the instructions in the Manual of Procedures.

6.3.2 Study Product Accountability

The study pharmacist will be responsible for maintaining an accurate record of the codes, inventory, and an accountability record of vaccine supplies for this study. Electronic documentation as well as paper copies may be used.

The VRC will receive copies of pharmacy records at the end of the study.

6.3.3 Disposal of Clinical Supplies

The empty vials and the unused portion of the vial should be discarded in a biohazard containment bag and incinerated. Any unopened vials (past the re-test date or otherwise) that remain will be destroyed at the discretion of the sponsor in accordance with policies that apply to investigational agents in Uganda. Partially used vials or expired prepared doses will not be administered to other participants or used for *in vitro* experimental studies. They will be disposed of in accordance with institutional pharmacy policy. Retest dates shall be updated as per analytical analyses of the IP. No IP shall be administered to a participant beyond the current retest date.

7.0 PHARMACOVIGILANCE, SAFETY, AND ADVERSE EVENT REPORTING

7.1 Definitions

An adverse event (AE) is any untoward medical occurrence in a clinical investigation participant administered a pharmaceutical product and does not necessarily have a causal relationship with this product. An AE can therefore be any unfavorable and unintended sign (including an abnormal laboratory finding), symptom, or disease temporally associated with the use of a medicinal (investigational) product, whether or not related to the medicinal (investigational) product. (International Conference on Harmonization (ICH) E6) (Synonym: Adverse Experience).

A serious adverse event (SAE): An adverse event or suspected adverse reaction is considered "serious" if, in the view of either the investigator or sponsor, it results in any of the following outcomes: Death, a life-threatening adverse event, inpatient hospitalization or prolongation of existing hospitalization, a persistent or significant incapacity or substantial disruption of the ability to conduct normal life functions, or a congenital anomaly/birth defect. Important medical events that may not result in death, be life-threatening, or require hospitalization may be considered serious when, based upon appropriate medical judgment, they may jeopardize the participant and may require medical or surgical intervention to prevent one of the outcomes listed in this definition. Examples of such medical events include allergic bronchospasm requiring intensive treatment in an emergency room or at home, blood dyscrasias or convulsions that do not result in inpatient hospitalization, or the development of drug dependency or drug abuse (21 CFR 312.32).

“Life-threatening” refers to an adverse event that at occurrence represents an immediate risk of death to the participant. An event that may cause death if it occurs in a more severe form is not considered life-threatening. Similarly, a hospital admission for an elective procedure is not considered an SAE.

All AEs will have their possible relationship to study vaccine assessed and will be graded according to the table for grading severity of adverse events (see Appendix 6). Arthralgia (joint pain) and arthritis AEs will be graded in accordance with the criteria in Appendix 7.

7.2 Adverse Event Grading and Recording

Recording of all AEs will occur during the period from study agent administration through 28 days after study agent administration. Solicited AEs will be recorded in the study database for 7 days after injection without the collection of attribute assessments. All unsolicited AEs and SAEs that occur during the period from study agent administration through 28 days after study agent administration will be recorded in the study database. After study day 28, only SAEs and new chronic medical conditions that require ongoing medical management will be recorded as AEs in the study database. Because this is an Ebola vaccine study, in the unlikely circumstance of Ebola virus disease (EVD) diagnosis in a study participant at any time throughout the study, this will be recorded on an “EVD CRF”, rather than an AE form, without requiring an investigator attribution (“relatedness to study agent”) or severity grade.

The FDA Guidance for Industry (September 2007): “Toxicity Grading Scale for Healthy Adult and Adolescent Volunteers Enrolled in Preventive Vaccine Clinical Trials” was adapted for the

severity grading of adverse events in this protocol. The FDA Guidance of Industry on toxicity grading scale is modified for criteria on absolute neutrophil counts and other parameters as described in Appendix 6, which also includes the definitions for severity grading parameters that do not have specific guidelines in the table. Due to the absence of specific grading criteria for arthralgias on the FDA toxicity grading scale, the “DAIDS AE Grading Table Corrected” (Version 2.1-July 2017) (Appendix 7) will be used to grade arthralgia AEs.

The clinical investigators will monitor and analyze study data including all AE and lab data as they become available and will make determinations regarding the severity of the adverse experiences and their relation to study product. AE CRFs will be completed by the research staff on a daily basis as the data become available from the clinic or laboratory. AEs are also subjected to analysis to identify those that may invoke study pause rules. To ensure that all AEs are captured in a timely manner, AE CRFs will be entered into the database within 24 hours. All other CRFs will be entered into the database within 3 business days. All CRFs will be subjected to analysis to identify AEs that may invoke study pause rules.

Although post injection reactogenicity (PIR)/Solicited AEs are documented separately from unsolicited AEs, they will be reported if they meet SAE or study pause rule definitions as noted below. Therefore the PI or designee must review both PIR and AE CRFs to ensure prompt and complete identification of all events that require expedited reporting as SAEs, study pause rules or other serious and unexpected events.

AEs will be followed by the clinical research team until resolved, and stability or chronicity has been established and documented.

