7.5 Criteria for Study Pause or Termination

The PI will closely monitor and analyze study data as they become available and will make determinations regarding the presence and severity of adverse events. The administration of study injections and new enrollments will be paused and the IND Sponsor will be promptly notified according to the following criteria:

- **One** (or more) participant experiences a **SAE** that is assessed as possibly, probably or definitely related to study agent, or
- **Two** (or more) participants experience the same **Grade 3 or 4** adverse event assessed as possibly, probably or definitely related to study agent.

Plan for Review of Pauses and Resuming Rules:

The study injections and enrollments would resume only if review of the adverse events that caused the pause resulted in a recommendation to permit further study injections and study enrollments. The reviews to make this decision will occur as follows:

Pauses for SAEs: The IND Sponsor and PSRT will consult with the SMC to conduct the review and make the decision to resume, amend or close the study for any SAEs that meet the criteria for pausing the study. The FDA will be notified of any SAE pause review.

Pauses for Grade 3 or 4 AEs: The IND Sponsor and PSRT will conduct the review and make the decision to consult the SMC, resume, amend or close the study for the Grade 3 or 4 events that meet the criteria for pausing the study. As part of the pause review, the reviewers will also advise on whether the study needs to be paused again for any subsequent Grade 3 or 4 event of the same type. The FDA will be notified of all Grade 3 or 4 pause reviews.

When indicated, safety data reports and changes in study status (study pauses) will be submitted to the IRB in accordance with institutional policy.

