APPENDIX 6: GRADING SEVERITY OF ADVERSE EVENTS

FDA Guidance for Industry (September 2007): “Toxicity Grading Scale for Healthy Adult and Adolescent Volunteers Enrolled in Preventive Vaccine Clinical Trials”

Modification to the FDA AE Grading Table

Individuals of African descent have lower neutrophil counts than individuals of other ethnicities. A study evaluating the reasons for ineligibility in phase I and II HIV vaccine trials in East Africa found that approximately one third of subjects were excluded because of neutropenia. The phase I and II studies used normal ranges from U.S. populations, not from African populations. If neutrophil ranges from East/South Africa populations were used instead, over one half of the subjects excluded because of hematologic abnormalities could have been included (ref.). Since this study will be conducted in part in East Africa, we will use the normal neutrophil range from East/South Africa ($1.0 - 5.3 \times 10^3$ cells/ul, (ref.) for subjects in Uganda or other subjects of African descent. Grades for absolute neutrophil count in these subjects will be as follows:

	Grade 1	Grade 2	Grade 3	Grade 4
Absolute Neutrophil Count (cells/ul)	750 – 999	500 – 749	250 – 499	< 250

For other subjects, the usual FDA AE grading scale will be used as follows:

	Grade 1	Grade 2	Grade 3	Grade 4
Absolute Neutrophil Count (cells/ul)	–1,500 – 2,000	1,000-1,499	500 - 999	< 500

Assessment of Causality Relationship of an Adverse Event (AE) to Study Vaccine:

The relationship between an AE and the vaccine will be assessed by the investigator on the basis of his or her clinical judgment and the definitions below.

- **Definitely Related.** The AE and administration of study agent are related in time, and a direct association can be demonstrated.
- **Probably Related.** The AE and administration of study agent are reasonably related in time, and the AE is more likely explained by study agent than other causes.
- **Possibly Related.** The AE and administration of study agent are reasonably related in time, but the AE can be explained equally well by causes other than study agent.
- **Not Related.** There is not a reasonable possibility that the AE is related to the study agent.

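### Can the Grade 3/4 pause rule work for solicited events if the database does not hold their relatedness?

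*Combined protocol and SAP*

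**What the plan says.** Section 7.2 of the protocol treats solicited reactions differently from other adverse events: "Solicited AEs will be recorded in the study database for 7 days after injection without the collection of attribute assessments". Later in the same section, solicited events are kept apart from unsolicited ones but "they will be reported if they meet SAE or study pause rule definitions as noted below". It continues: "Therefore the PI or designee must review both PIR and AE CRFs to ensure prompt and complete identification of all events".

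Section 7.5 has two triggers. One is a single SAE judged related. The other is two or more participants with the same Grade 3 or 4 "adverse event assessed as possibly, probably or definitely related to study agent".

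Section 7.1 makes a general statement with no exception for solicited events: "All AEs will have their possible relationship to study vaccine assessed". Section 7.2 adds: "All CRFs will be subjected to analysis to identify AEs that may invoke study pause rules". Section 8.3.4 says that pause events will be found by database functions together with review by safety staff. Section 8.3.2 tabulates reactogenicity by group and severity, and other adverse events by relationship as well.

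**The concern.** The second trigger needs the same event, Grade 3 or 4, a judgment of relatedness, and at least two participants. For a solicited reaction the database holds the event and the grade but, read literally, not the relatedness. Section 7.1 seems to promise an assessment that Section 7.2 then declines to collect.

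The rule also links two participants, perhaps weeks apart. The first severe reaction does not trigger anything, so nothing in the visible text forces a written relatedness call on it before the second arrives. A judgment of not related keeps injections going and need leave no trace in the database. Section 7.2.1 shows that the protocol can state a default when it wants one, since it presumes gradable respiratory rates to be unrelated unless there is evidence of pathology. It gives no default for solicited reactions.

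The setting adds weight. This is a dose escalation, and Section 1.2.2 expects about 70% of participants to have some systemic reaction. If a pause could be missed for want of a data field, that would be a safety matter.

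**Working it through.** There is no stated figure to reproduce. The check is to follow a solicited event through the text.

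**1. What is not collected.** Attribute assessments are not defined, but relatedness is the natural meaning. Section 7.2 puts an Ebola diagnosis on its own form "rather than an AE form, without requiring an investigator attribution", and explains attribution there as relatedness. Appendix 6 uses the same word for the related/not related classification. Severity cannot be meant, because the reactogenicity tables in Section 8.3.2 need it. The premise of the concern is accepted.

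**2. Whether the judgment is made.** Section 7.1 requires it for all adverse events, Section 7.2 has the clinical investigators determine relation to product, and Appendix 6 says: "The relationship between an AE and the vaccine will be assessed by the investigator on the basis of his or her clinical judgment". Section 7.1 is about making the judgment and Section 7.2 is about storing it in the database. Both can be followed.

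**3. Whether a database screen can miss a pause event.** Let G be the participants with a given solicited event at Grade 3 or 4, and R those in G whose event is judged related. R is a subset of G, so the count in R cannot exceed the count in G. If R reaches two, G has reached two already. A screen on grade alone therefore flags every case that meets the rule, plus some that do not, and people settle relatedness. The error is towards over-flagging.

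**4. Which events are left.** There are ten diary items: temperature, six general symptoms and three injection-site items. For six of them (local pain, headache, muscle aches, nausea, feeling unwell, chills), Grade 4 in Appendix 6 involves hospitalization, using the general rows where no specific row exists. Inpatient hospitalization is an SAE under Section 7.1. Such events are reported to the sponsor within 24 hours, with a written report within 3 working days (Section 7.6.2). They fall under the one-SAE trigger in Section 7.5, and the research monitor must comment on relationship (Appendix 9). What remains is non-serious Grade 3 events, plus Grade 4 fever, joint pain and local necrosis where these are not serious.

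**5. What trace is left.** A pause brings sponsor notification, review by the sponsor and the safety review team, and notice to the FDA (Section 7.5), with further notices under Sections 7.6.4, 7.6.5 and 11.4. Only a judgment of not related on a non-serious event may go without a record that the visible text requires.

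**6. How much turns on the judgment.** The documents give no Grade 3/4 rate, so any figure is an assumption. With rate p for one particular event and n participants, the chance that at least two have it is

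1 − (1 − p)^n − n·p·(1 − p)^(n−1).

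| Assumed p | n = 20 | n = 40 |
|---|---|---|
| 5% | 1 − 0.3585 − 0.3774 = 0.264 | 1 − 0.1285 − 0.2706 = 0.601 |
| 10% | 1 − 0.1216 − 0.2702 = 0.608 | 1 − 0.0148 − 0.0657 = 0.920 |

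Section 7.5 sets no limit by group, so n = 40 is relevant as well as n = 20. If the rate is 10% and half of the events are judged related, the related rate is 5%. The chance of meeting the rule is then 26% rather than 61% in one group, a gap of 34 points (0.6083 − 0.2642 = 0.3441), and 60% rather than 92% in the whole study. These figures show that the judgment can decide whether a pause occurs. They say nothing about pauses missed because of where it is stored.

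**The case for a change.** The best case for a change is that a criterion able to halt the study should be auditable from the study data. Section 8.3.4 leans partly on the database, and for solicited events the database can test grade but not relatedness. The people-based safeguards ensure a judgment without saying where it is kept. Pause and SAE reports document events that were judged to qualify, whereas an audit would most want to see the calls that did not. One form field for a few events would cost little.

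Part of this stands. The visible text names no place for the relatedness call on a non-serious Grade 3 or 4 solicited event, and no default is stated. The rest does not carry to a change. Section 8.3.4 pairs the database with human review and does not ask the database to test every element of the rule. Review of the reactogenicity forms is mandatory. The safety review team sees aggregate data weekly during the vaccination period and at three staged reviews (Section 7.3), none of which depends on a stored attribution. The reactogenicity form itself is not in the documents, and the diary card is only a memory aid, so the absence of a place for the judgment cannot be shown.

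**Conclusion.** No change to the plan is needed. Followed as written, the rule works: relatedness is judged, the relevant forms must be read, and the missing field makes a grade screen over-inclusive rather than blind. The pause rule, its threshold and every planned endpoint table are unaffected. The remaining gap is a matter of record-keeping for non-serious Grade 3 or 4 solicited events, chiefly those judged not related, and study staff can be expected to settle it in their forms or source notes.

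This rests on three assumptions: attribute assessments means relatedness; severity of solicited events is in the database, as Section 8.3.2 requires; and the form review in Section 7.2 is carried out. If attribute assessments means something else, the concern falls away altogether. The probabilities above depend on assumed rates and should not be read as a risk of missed pauses.

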Follow-up on participant well-being will be performed by telephone or clinic visit on the day following vaccination and by clinic visit on Day 3 following the injection to assess their clinical status. Participants may call or come to the clinic at any time-point for evaluation, if they experience unusual, moderate or severe signs and symptoms. Diary cards will be reviewed with the clinician at any visit from day of vaccination through the first study visit following completion of the diary card. If upon reviewing the clinician finds that general symptom or injection site symptom information (except swelling or redness measurements) is missing from the diary cards, the participant will be asked to provide the missing information to the best of their recollection.

At every visit through study day 28, all participants will be asked about other interim adverse experiences, which will be recorded in source documents and entered into the study database within 3 business days. After study day 28, only serious adverse events and new chronic medical conditions that require ongoing medical management will be recorded in source documents and entered into the database, through the last study visit. All other adverse events will be recorded on source documents only. The PI or designee will assess the relationship of the study product to the events.

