8.3.4 Interim Analyses

Safety Reviews: The PSRT will review safety data routinely throughout the study. The study will utilize both electronic database features and reviews by designated safety review personnel to identify in a timely manner if any of the safety pause rules of the study are met. The SMC will review study data on an annual basis from the time the study opened.

Immunogenicity Review: Periodic analyses of immunogenicity for each group may be performed during the study for the purpose of informing future vaccine-related decisions in a timely manner once there are at least 3 participants in the group with the 4 weeks post vaccination follow-up completed. The results will not influence the conduct of the trial in terms of early termination or later safety or immunogenicity endpoint assessments.

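### The Grade 3/4 pause rule has no time window, but after Day 28 related non-serious events get no AE record that the systematic pause screen can count

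*Combined protocol and SAP*

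**What the plan says.** **The rule.** Under Section 7.5, "The administration of study injections and new enrollments will be paused" if two or more participants have the same Grade 3 or 4 "adverse event assessed as possibly, probably or definitely related to study agent". The section sets no end date, dose-group restriction or seriousness condition for this limb.

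**The record.** Section 7.2 states: "After study day 28, only SAEs and new chronic medical conditions that require ongoing medical management will be recorded as AEs in the study database". Section 5.3.1 agrees and adds: "All other adverse events will be recorded on source documents only".

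**The screen.** Section 7.2 states: "All CRFs will be subjected to analysis to identify AEs that may invoke study pause rules". It also has the PI or designee go through the reactogenicity and AE CRFs for the same purpose. Section 8.3.4 relies on database features together with designated safety staff "to identify in a timely manner if any of the safety pause rules of the study are met".

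**Routes without a Day 28 limit.** Section 7.5 says "The PI will closely monitor and analyze study data as they become available". Directly after the source-only sentence, Section 5.3.1 says "The PI or designee will assess the relationship of the study product to the events". Section 7.3 gives the PSRT all AEs to review, but the expedited pause review that it names is for SAEs.

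**The concern.** The rule counts events over an open period, while the records that feed the systematic count close at Day 28 for everything except SAEs and new chronic conditions. A transient related Grade 3 event on Day 40 qualifies under Section 7.5, yet no AE CRF is created for it.

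The timing matters because the groups are dosed in sequence: Group 1 follow-up after Day 28 can coincide with dosing at a level ten times higher. Two late Group 1 events of one type, or one late Group 1 event and one early Group 2 event, meet the rule. The screen would see none of the first pair and only one of the second.

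Other parts of the protocol appear to assume that such events are visible. Section 7.5 asks those reviewing a pause to advise on later Grade 3/4 events of the same type. Section 5.4 updates concomitant medication in the database for a related AE, with no Day 28 limit.

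**Working it through.** The plan gives no figure for this rule, so there is none to reproduce. Two questions can be checked: which events lack a countable record, and whether Group 2 is still being dosed when they could occur.

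**1. Which events.** After Day 28:
- SAEs are entered, and one related SAE pauses the study by itself.
- New chronic conditions needing ongoing management are entered.
- Laboratory values are probably in the database. Appendix 1 schedules CBC, creatinine and ALT at Day 56, Section 8.3.2 plots values measured during the study, and Section 7.2 screens all CRFs. That these values sit on CRFs is an inference. The rule also needs a relatedness judgement, and no AE record carries one for a late non-serious, non-chronic laboratory event.
- Other related Grade 3/4 clinical events are in source documents only.

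**2. Overlap with Group 2 dosing.** Inputs from Sections 4.0 and 7.3: three sentinels per group at no more than one per day, at least 7 days of follow-up before each review, then 17 more per group. No rate is given for the 17; Section 1.2.2 only describes enrolment as slow. Assumptions: rate r per day for the 17, and v days of extra delay at each review. The first dose is trial day 0.

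With f = floor(16/r):
- Group 1 sentinels: days 0, 1, 2. The other 17: days 9 + v + floor(i/r), i = 0 to 16.
- Last Group 1 dose: 9 + v + f.
- First Group 2 dose: (9 + v + f) + 7 + v = 16 + 2v + f.
- Last Group 2 dose: E = (16 + 2v + f) + 9 + v + f = 25 + 3v + 2f.
- A Group 1 participant dosed on day d is past Day 28 at the last Group 2 dose if d + 28 < E.

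| r per day | v | f | First Group 2 dose | E | Group 1 past Day 28 at first Group 2 dose | At last Group 2 dose | Group 1 at Day 56 bloods by E |
|---|---|---|---|---|---|---|---|
| 17 | 0 | 0 | 16 | 25 | 0 | 0 | 0 |
| 3 | 0 | 5 | 21 | 35 | 0 | 3 | 0 |
| 2 | 0 | 8 | 24 | 41 | 0 | 11 | 0 |
| 1 | 0 | 16 | 32 | 57 | 3 | 20 | 2 |
| 1 | 7 | 16 | 46 | 78 | 5 | 20 | 10 |
| 17 | 7 | 0 | 30 | 46 | 2 | 20 | 0 |

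Example at 2 per day: d + 28 < 41 requires d < 13. That gives the 3 sentinels plus two per day on days 9 to 12, so 3 + 8 = 11. At 1 per day with no delay, Group 1 time after Day 28 but before the last Group 2 dose is (29 + 28 + 27) + (20 + 19 + … + 4) = 84 + 204 = 288 person-days. The last row shows that review delay alone can produce the overlap.

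**3. Illustration only.** The documents give no rate for late events. If each of 20 Group 1 participants had a late related Grade 3/4 event of one type with probability p, the chance of two or more is 1 − (1 − p)^20 − 20p(1 − p)^19. This is 1.7% at p = 1%, 6.0% at 2% and 26.4% at 5%.

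**The case against.** The strongest reply is that source-only recording does not hide an event from people. Under Section 7.2 the investigators follow all AE and laboratory data and judge severity and relatedness. Section 7.5 has the PI apply the rule to study data, not only to database records. Section 7.3 gives the PSRT all AEs, with the aggregate reports as an addition. Section 8.3.4 pairs the database with designated staff. Appendix 9 has AEs reach the IND Medical Officer through the PI, and Section 7.6.4 sends unexpected events above moderate severity to the IRB and NDA within 7 days. None of these stops at Day 28. This stands: a reader might infer that such events vanish, or that only the PI's recollection links them, and the documents do not support that. What they do not say is how a source-only event reaches these people or is counted toward two.

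A reader might also infer that a Day 56 platelet or ALT result can never reach the pause check. That is not supported either. The values are collected for analysis, Section 5.3.3 requires a repeat of any Grade 3/4 result within 48 hours, and Section 7.1 lists blood dyscrasias among possible SAEs. For laboratory events the gap is the missing relatedness record.

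Nor does the overlap arise on every schedule. On the fastest it is nil. Allowing one extra day at each review gives E = 25 + 3 = 28, when the first sentinel has reached Day 28 but not passed it. The Day 168 CBC adds little, because a pause stops only injections and enrolment.

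Finally, the remaining events are narrow: late, related, Grade 3/4, non-serious, non-chronic, and of one type in two participants before dosing ends. Section 1.2.2 describes reactogenicity as typically on the day of vaccination or the day after. This limits the size of the problem but does not remove the mismatch.

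**Conclusion.** The point holds as a mismatch between an open-ended pause rule and a database cut at Day 28. Related non-serious, non-chronic Grade 3/4 events after Day 28 fall outside the systematic screen and depend on manual review, with no stated way to count them.

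The exposure ends at the last Group 2 injection. It ranges from 0 of 20 Group 1 participants on the fastest permitted schedule to 3, 11 and 20 of 20 at 3, 2 and 1 per day without review delay. The rates are assumptions; the slower ones fit the plan's own description of enrolment. The expected number of such events is unknown and probably small. This is a worthwhile, inexpensive improvement to safety monitoring, not a failure of it.

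**What to change.** Reconcile Sections 5.3.1, 7.2, 7.3, 7.5 and 8.3.4. In Sections 5.3.1 and 7.2, add one category to what is entered after Day 28: any Grade 3 or 4 AE, clinical or laboratory, assessed as possibly, probably or definitely related. Enter it on an AE CRF within the 24 hours that Section 7.2 already sets, at least until the last Group 2 injection. State in Sections 7.3 and 8.3.4 that these records are part of the pause screen and PSRT review. List them separately so that the Day 28 AE endpoint in Section 3.1 is unaffected. The Section 7.5 criteria stay as they are; whether the rule should carry a time window is for the sponsor.

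Cost: a short addition to each section and a few extra CRFs for events already assessed and written in source. The downside is slightly uneven AE capture after Day 28, since related Grade 3/4 events would be in the database and other non-serious events would not.
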